## 1 PROTOCOL SUMMARY

[figure not shown]
### 1.1 Synopsis

Title:	Mechanisms Of Change in Adolescent Pain Self-management (MOCAS)
Grant Number:	R21NR017312
Study Description:	
Objectives*:	
Primary Objective: The study objective is to characterize how sleep deficiency influences youth's ability to engage with, implement, and benefit from pain self-management intervention.
 
Secondary Objectives:

Endpoints*:	
Primary Endpoint: 6 months
 
Secondary Endpoints: Immediate post-treatment (10 weeks)

Study Population:	The study population includes 80 youth with chronic musculoskeletal, head, or abdominal pain (pain for longer than 3 months) who are ages 12-17 years. Both males and females will be included. All youth will have received an evaluation for complex chronic pain in the Seattle Children's Pain Clinic.
Phase* or Stage:	Phase 1
Description of Sites/Facilities Enrolling Participants:	The study site is Seattle Children's Hospital. No sites outside of the United States will be included
Description of Study Intervention/Experimental Manipulation:	The study intervention is a pain self-management intervention called WebMAP (Web-based management of adolescent pain) delivered via the internet. The length of the intervention is 8 weeks and youth and parents complete one 15-minute module per week. The eight child modules include: 1) education about chronic pain, 2) recognizing stress and negative emotions, 3) deep breathing and relaxation, 4) implementing coping skills at school, 5) cognitive skills (e.g., reducing negative thoughts), 6) lifestyle interventions, 7) staying active (e.g., pleasant activity scheduling), 8) relapse prevention. The eight parent modules are: 1) education about chronic pain, 2) recognizing stress and negative emotions, 3) operant strategies I (using attention and praise to increase coping), 4) operant strategies II (using rewards to increase positive coping and reach school goals), 5) modeling, 6) lifestyle, 7) communication, 8) relapse prevention.
Study Duration*:	The duration of the study is 24 months.

**Participant Duration:** Participant duration is 6 months.

## 1.2 Schema

### *Study Flow*

## 1.3 Schedule of Activities

	Pre-Screening	Consent	Time 1	Time 2	Time 3	Time 4
EMR Review	X					
Eligibility						
Informed Consent		X				
Demographics			X			
Sleep assessment			X		X	X
Outcome evaluation			X		X	X
Mediator evaluation				X		
Intervention			X	X		
Adverse events reporting				X	X	X

## 2 INTRODUCTION

### 2.1 Study Rationale

Five to 8% of youth report severe chronic pain and disability. Pediatric chronic pain is costly to society, with estimates of \$19.5 billion/year spent in the US on direct healthcare costs. History of childhood chronic pain places youth at risk for a lifelong pattern of pain, disability and high health care costs in adulthood. Thus, finding effective methods that support youth in pain self-management is a priority. Our preliminary data suggest that youth with greater sleep deficiency find pain self-management intervention less acceptable and make fewer gains in pain-related outcomes, indicating that sleep may represent an overlooked health factor affecting self-management skills. Although progress has been made in establishing pain self-management interventions for youth, treatments produce wide variability in patient response and do not target sleep deficiency.

Therefore, the objective of this application is to characterize how sleep deficiency influences youth's ability to engage with, implement, and benefit from a pain self-management intervention. We will study a cohort of 80 youth receiving internet-delivered pain self-management over an 8-week period. Sleep deficiency will be comprehensively assessed with subjective measures, daily sleep logs, and ambulatory actigraphy monitoring to measure disrupted sleep, amount of sleep, sleep quality, and insomnia symptoms. Following the recommended Common Data Elements for self-management we measure three self-management processes including patient activation, pain self-efficacy, and self-management skills, and assess patient-reported treatment engagement and health (global health, fatigue) and pain outcomes (pain symptoms, pain-related disability). Positive and negative affect and executive functioning will be assessed as potential mediators. The next steps in this research program are to enhance the effectiveness of pain self-management interventions by addressing co-occurring sleep deficiency. Specific aims and hypotheses are:

**Aim 1. Characterize the relationship between baseline sleep deficiency and self-management processes.** H1. Greater baseline sleep deficiency (shorter sleep duration, poorer sleep quality, increased insomnia symptoms, greater wake time after sleep onset) will be associated with lower activation, lower pain self-efficacy, and lower use of self-management skills from pre- to post-treatment. H2. Positive and negative affect and executive functioning will mediate the relationship between sleep deficiency and self-management processes.

**Aim 2. Determine the effect of baseline sleep deficiency on treatment acceptability, engagement, and benefit from an internet-delivered pain self-management intervention.** H3. Greater sleep deficiency will be associated with lower perceptions of treatment acceptability and engagement (fewer logins, fewer completed treatment modules and assignments). H4. Greater sleep deficiency will be associated with less benefit (fewer improvements) in ratings of global health, fatigue, pain symptoms, and pain-related disability following pain self-management intervention. H5. Positive and negative affect and executive functioning will mediate the relationship between sleep deficiency and treatment acceptability, engagement and benefit.

## 2.2 Background

**Chronic Pain and Sleep Deficiency.** Pain that persists for longer than three months is common; 5-8% of youth report severe and disabling chronic pain (1). These youth demonstrate elevated anxiety and depressive symptoms as well as difficulty attending school, participating in sports and physical activities, and maintaining social participation (2). Sleep deficiency is defined as a deficit in the quantity or quality of sleep obtained versus the amount needed for optimal health, performance and well-being (3). Sleep deficiency is highly co-morbid, affecting over half of youth with chronic pain (4, 5). Sleep deficiency is associated with diminished physical function, poorer quality of life, and increased anxiety and depressive symptoms (6, 7). Sleep problems comorbid with chronic pain are also recognized as costly in terms of prescription medications, health care use, and lost work productivity (8, 9), compounding the negative financial toll of chronic pain.

**The interrelationship between sleep deficiency and pain.** Early models described a bidirectional relationship between pain and sleep (10), where uncontrolled pain can cause sleep disruptions, and in turn, disturbed sleep can enhance pain sensitivity (11). Recent research has demonstrated that more studies now support the direction of sleep impacting pain than vice versa. That is, sleep deficiency has now been shown to lead to subsequent increased pain. Findings are from studies using experimental and self-report designs in multiple samples across childhood and adulthood (12), highlighting its relevance in chronic pain treatment.

**Self-Management Interventions for Pediatric Chronic Pain.** There are compelling longitudinal data demonstrating that childhood chronic pain places individuals at significant risk for developing or continuing with chronic pain into adulthood (13). Thus, learning effective pain self-management in childhood may be critical for preventing or lessening the enormous economic and societal impact of adult chronic pain. Self-management interventions including cognitive-behavioral therapy (CBT) offer safe and effective alternatives to medications for chronic pain and progress has been made toward developing effective self-management pain interventions for children. *Our own internet-delivered pain self-management program (WebMAP) has shown efficacy in reducing children's pain-related disability, anxiety, and depressive symptoms (14). However, treatment produces small to moderate effect sizes and there is wide variability in treatment response.* To date, very little research has been conducted on moderators or mediators of treatment benefit, and no consistent variables have been identified. Thus there is limited empirical understanding of how to enhance the effectiveness of pain self-management interventions for children.

**Conceptual Model of the Effect of Sleep Deficiency on Pain Self-Management.** While conceptualizations of self-management vary, the construct generally refers to the daily activities that individuals must perform to keep their illness under control, minimize its impact on their physical health and functioning, and cope with any comorbid or resulting psychological symptoms (15, 16). Successful self-management in youth involves fostering patient and family self-efficacy and motivation for making behavioral changes.

**We propose that sleep deficiency is a modifiable pathway that may influence success of pain self-management.** Sleep deficiency is associated with general deficits in higher-order and complex cognitive functions and reduced self-regulatory skills (e.g., 17), which may influence self-management tasks. As reviewed by Stickgold and Walker (2013), sleep (a) enhances cognitive flexibility in problem solving (19, 20), (b) assists in the integration of new learned information (21), and (c) is critical for promoting memory associations (22). Sleep also affects elements of self-control such as subjective effort, perceived exertion, and choice (23) and short sleep duration increases negative affect and decreases positive affect (24). *Because self-management relies on organization, memory, and behavioral activation, we hypothesize that positive and negative affect and executive function will mediate the relationship between sleep deficiency and self-management.* Relevant research in other pediatric chronic conditions has examined effects of sleep deficiency on self-management behaviors in youth. For example, in a study in youth with diabetes, greater sleep deficiency was related to reduced treatment adherence (25). Similarly, in youth receiving a physical activity self-management intervention, greater sleep deficiency was related to reduced efforts at self-monitoring, goal-setting, and social support behaviors (26). Thus, our scientific premise is that in addition to the direct effect of sleep on pain and functioning, sleep deficiency also decreases youth's acceptability of treatment, motivation to engage with treatment, and to implement self-management tasks and behaviors.

This scientific premise is supported by our own pilot data showing that several aspects of sleep deficiency are related to treatment acceptability and outcomes. Specifically, in pilot work we found that shorter sleep duration at baseline predicted reduced benefit (i.e., less improvement in pain-related disability) with a self-management intervention for chronic pain (27) and that poor baseline sleep quality was associated with lower youth perception of overall treatment acceptability. However, to date, studies have not determined the impact of sleep deficiency on pediatric pain self-management.

**Use of the Internet to Deliver Pain Self-Management.** Even though pain self-management has been shown effective, major barriers exist for families to access this care due to the geographical distance and limited scheduling that prevents most patients from receiving psychological intervention (28). Availability of information and communication technology has expanded opportunities for intervening with families remotely, and internet-delivered chronic pain self-management interventions have been found effective in both adult and pediatric populations (29) for managing pain and disability. We have had tremendous success in our research studies reaching families using Internet and smartphone technologies.

## 2.3 Risk/Benefit Assessment

### 2.3.1 Known Potential Risks

Risks for this study concern the potential for emotional distress, loss of confidentiality, and a burdensome time commitment. Study questionnaires and the websites contain material concerning pain and psychosocial functioning that may elicit emotional discomfort. To mitigate this discomfort, all

aspects of the study are voluntary. We will inform participants that if they feel uncomfortable completing any part of the study, they can let us know and stop participating in that part of the study. Participants will also be informed that their data will be safeguarded to preserve confidentiality. Participants will be instructed to access the programs in a safe place (e.g. not while driving or completing other tasks). Burden related to the length of the questionnaire assessments and lessons will be kept at a minimum, such that parents and adolescents will likely spend about 20-30 minutes completing questionnaires at each time point, and 20-30 minutes for each lesson. Daily assessments take ~2 minutes. Because the data collection system, REDCap, will save and store responses from questionnaires, children and parents may log on and off at their convenience to complete assessments. Due to the fact that we are acquiring information from children and parents online, we are sensitive to the need to carefully safeguard all data entered on the app. Protected health information will not be collected on the app. All study data will be safeguarded using secure password-protected servers at Seattle Children's Hospital. The primary source of data will come from questionnaires, which will be collected in an encrypted manner and stored in secure password-protected databases. All contact information from the referrals will be stored in a secure database within the PIs' research lab at Seattle Children's Research Institute (SCRI). The participant codebook will be kept on a password protected server to which only study staff has access.

### **2.3.2 Known Potential Benefits**

Participation in this research may or may not benefit the participant. Completion of the CBT program delivered via the website may help to reduce pain and improve functioning in adolescents. Information collected will provide useful data regarding how sleep influences response to psychosocial treatment for chronic pain in adolescents that may inform implementation of effective treatments for adolescents with pain. After the study is completed and results are published, we will send participants an email about what we learned.

### **2.3.3 Assessment of Potential Risks and Benefits**

The potential risks of participation to the participants are considered to be minimal in relation to the potential gain in critical knowledge of how sleep influences the benefits from psychosocial intervention to improve pain outcomes in youth.

### 3 OBJECTIVES AND ENDPOINTS

OBJECTIVES	ENDPOINTS	TIMEFRAME
Characterize the relationship between baseline sleep deficiency and self-management processes.	The Pain Self-Efficacy Scale (45) is a 7-item measure that assesses the child's beliefs in carrying out activities when in pain. The scale has demonstrated good internal consistency, cross-informant reliability with parent report, and strong construct validity.	T1, T3, T4
	The Patient Activation Measure (46) is a 13-item questionnaire that assesses an individual's knowledge, skill and confidence for managing their health and health care. The PAM uses a 0-100 scale resulting in 4 levels of activation, from low (1) to high (4). The measure is not disease specific, and has been successfully used with a wide variety of chronic conditions. Although developed for adults, the PAM has been used in children ages 12 and above, is reliable, and shows strong construct validity. Self-management skills.	T1, T3, T4
Determine the effect of baseline sleep deficiency on treatment acceptability, engagement, and benefit from an internet-delivered pain self-management intervention.	Pain intensity will be measured using the 11-point NRS (numerical rating scale) completed by children via daily diary assessments over a 7-day period. Scores are averaged at each timeframe with higher scores indicating higher pain intensity.	T1, T3, T4
	The Child Activity Limitations Interview (CALI-9) is a daily diary validated to assess perceived difficulty in completing 9 daily activities as a measure of pain-related disability. Responses are rated on a 5-point scale (0-4) with higher scores indicating greater perceived difficulty with activities. Youth will provide ratings daily for 7 days on their online diaries at each assessment period. Mean total activity limitations across the reporting period is used in analyses, with higher scores indicating greater disability.	T1, T3, T4

## 4 STUDY DESIGN

### 4.1 Overall Design

This is a single arm trial to identify mechanisms of response to CBT intervention. All youth will receive active intervention, the Web-based Management of Adolescent Pain intervention.

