### 6.2 Measures to Minimize Bias: Randomization and Blinding

After baseline assessment is completed, participants will receive access to the study intervention. Research staff will set up accounts and instruct the participants regarding how to access the WebMAP intervention. There is no masking as this is not a randomized trial.

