## 9 STATISTICAL CONSIDERATIONS

### 9.1 Statistical Hypotheses

- Primary Objective:

**Aim 1. Characterize the relationship between baseline sleep deficiency and self-management processes.** H1. Greater baseline sleep deficiency (shorter sleep duration, poorer sleep quality, increased insomnia symptoms, greater wake time after sleep onset) will be associated with lower activation, lower pain self-efficacy, and lower use of self-management skills from pre- to post-treatment. H2. Positive and negative affect and executive functioning will mediate the relationship between sleep deficiency and self-management processes.

- Secondary Objective:

**Aim 2. Determine the effect of baseline sleep deficiency on treatment acceptability, engagement, and benefit from an internet-delivered pain self-management intervention.** H3. Greater sleep deficiency will be associated with lower perceptions of treatment acceptability and engagement (fewer logins, fewer completed treatment modules and assignments). H4. Greater sleep deficiency will be associated with less benefit (fewer improvements) in ratings of global health, fatigue, pain symptoms, and pain-related disability following pain self-management intervention. H5. Positive and negative affect and executive functioning will mediate the relationship between sleep deficiency and treatment acceptability, engagement and benefit.

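### The single-arm design can show that baseline sleep predicts change during WebMAP, but not that sleep alters treatment benefit (H4, the benefit part of H5) or is a mechanism of response to CBT

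*Combined protocol and SAP*

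**What the plan says.** Section 4.1 describes the design in two sentences: "This is a single arm trial to identify mechanisms of response to CBT intervention" and "All youth will receive active intervention, the Web-based Management of Adolescent Pain intervention". Section 6.2 adds "There is no masking as this is not a randomized trial". Aim 2, in Sections 2.1 and 9.1, is to "Determine the effect of baseline sleep deficiency on treatment acceptability, engagement, and benefit from an internet-delivered pain self-management intervention". The hypothesis on benefit, H4, reads "Greater sleep deficiency will be associated with less benefit (fewer improvements) in ratings of global health, fatigue, pain symptoms, and pain-related disability". H5 adds mediation by affect and executive functioning, for benefit as well as for acceptability and engagement.

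Section 9.3 plans latent growth models in the treated cohort, adjusted for age, sex and the site of pain. The expected finding is that more sleep deficiency at the start goes with flatter improvement.

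Section 4.2 gives the reason for having no control: earlier randomised trials have shown that the approach works, and the present aim is to learn what sleep does to self-management behaviour rather than to test efficacy. Section 2.1 names the next step of the programme as to "enhance the effectiveness of pain self-management interventions by addressing co-occurring sleep deficiency".

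**The concern.** *Benefit from an intervention* and *mechanisms of response* are statements about what the treatment causes. A slope of change on baseline sleep among treated youth is a statement about who improves. The two coincide only if sleep would not predict change without the programme.

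The protocol's own background makes that doubtful. Section 2.2 reports that poor sleep precedes worse pain, and its premise includes a direct path from sleep to pain and function, separate from the path through self-management. Section 8.2 adds that usual medical care continues during the study.

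A supported H4 could be read as showing that poor sleep blunts WebMAP, and so that treating sleep would make WebMAP work better. The same data would arise if poor sleepers improve less under any care. Neither discussion of pitfalls in Section 9.3 mentions the missing comparator.

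**Working it through.** **The plan's own figures.** Section 9.3 projects 80 × 0.90 = 72 completers, which reproduces. Section 9.2 gives power .80 at N = 75 for a predictor of the slope worth R² = .06. That simulation cannot be rerun, because the growth variances, residual variances, reliabilities and alpha for Aim 2 are not stated. An ordinary regression proxy uses f² = R²/(1 − R²) = .06/.94 = 0.0638 and noncentrality 75 × 0.0638 = 4.79. It gives power of about 0.58 at two-sided alpha .05 and 0.70 at .10. Because the inputs are undisclosed, this leaves the .80 unverified rather than shown wrong. The point here does not depend on it.

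**The model.** Write improvement as

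improvement = μ + (b_p + b_m × T) × sleep + error,

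where sleep is standardised deficiency, b_p is the prognostic slope, b_m is the modification of the treatment effect, and T is 1 if treated. With T = 1 for everyone, the data inform only b_p + b_m.

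**Three cases with the same sum.** Take b_p + b_m = −√.06 = −0.245 and error variance .94. Each case has 20,000 simulated trials, tested at two-sided alpha .05 (an assumption).

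| Case | b_p | b_m | Mean slope, N = 75 | Rejection, N = 75 | Rejection, N = 72 |
|---|---|---|---|---|---|
| Prognosis only | −0.245 | 0 | −0.245 | 0.569 | 0.556 |
| Modification only | 0 | −0.245 | −0.245 | 0.571 | 0.553 |
| Worse course, but poor sleepers benefit more | −0.490 | +0.245 | −0.246 | 0.572 | 0.551 |

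The differences are simulation noise. The third case has modification in the opposite direction to H4, yet looks like support for H4. A larger sample narrows the interval around the sum and says nothing about its parts. The growth model separates starting level from change. It does not separate change that would have happened anyway from change due to treatment.

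**How often this would matter.** If sleep were purely prognostic at R² = .06, H4 would appear supported with probability .80 on the plan's figure, or about 0.57 on the simulation.

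**Which outcomes are affected.**
- Pain, disability, fatigue and global health change with or without WebMAP, so H4 and the benefit part of H5 are affected.
- Acceptability, logins, modules and assignments have no untreated counterpart. H3 and the matching part of H5 do not need a control for this purpose, although sleep may still be confounded with other baseline traits.

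**The case against.** The best defence is that the working hypotheses are already modest. H4 speaks of association and glosses benefit as improvement. The expected results in Section 9.3 are descriptive, and no sleep-by-treatment interaction is claimed. Section 4.2 shows that the single arm was a deliberate choice for a small study, and Aim 2 is the secondary objective in Section 9.1. All of this stands, and it makes the remedy one of wording. It does not remove the problem. Section 4.2 settles average efficacy, not whether the effect varies with sleep, and H4's outcomes are not self-management behaviours. Section 4.1 and the Aim 2 statement still announce a mechanism and an effect on benefit.

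A reader might infer more than the documents support:
- *That sleep is known to predict untreated change.* Section 2.2 makes this plausible, not established. A stable effect of sleep on pain level would fall on the growth-model intercept rather than the slope, and the statement about later pain does not cover fatigue or global health.
- *That regression to the mean, from the entry threshold of 5 on the Brief Pain Inventory items, biases the result.* It shifts average change. It would distort the sleep slope only if it differed by sleep, which nothing in the documents shows. The pain and disability outcomes also come from separate 7-day diaries.
- *That the prognostic share must lie somewhere between none and all of the slope.* The third case above breaks that limit: its prognostic part is 0.490/0.245 = 2 times the observed slope.

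**Conclusion.** The concern holds for the wording of Section 4.1, the benefit part of Aim 2, H4 and the benefit part of H5. The association of baseline sleep with change under treatment can be estimated. Its reading as altered benefit or as a mechanism of response cannot be supported at any sample size, and even the direction of modification is open. This rests on the absence of any concurrent, historical or external comparator in the plan, and on prognosis by sleep being possible, which the protocol's own background suggests. The numerical illustration further assumes a linear model, standardised sleep and R² = .06.

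It would go too far to say that Aim 2 as a whole fails, since acceptability and engagement are untouched. It would also go too far to say that a purely prognostic effect is bound to make H4 look supported: that is a matter of power. Nor do the documents show that the next step in Section 2.1 depends on H4; they present it as the direction of the programme.

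**What to change.** In Section 4.1, the benefit part of Aim 2 wherever it appears (2.1, 3, 9.1, 9.3), H4, the benefit part of H5 and the Aim 2 interpretation in 9.3, restate the target as the association of baseline sleep deficiency with change during and after WebMAP. Leave the acceptability and engagement wording as it is. Add to 9.3 a sentence such as: *Because there is no comparator, this association may reflect the course that would have occurred without WebMAP. It will not be reported as sleep modifying treatment benefit or as a mechanism of response to CBT.*

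Optionally, look to the group's earlier randomised trial of online CBT, which Section 2.2 cites for the finding that "shorter sleep duration at baseline predicted reduced benefit". If baseline sleep was measured in its control arm and the data are available, fit the same sleep-to-change model by arm. The documents say neither. A null comparison would be weak evidence. With 1:1 allocation, two-sided alpha .05 and pure modification worth R² = .06 in the treated arm, power for the sleep-by-arm test is about 0.18 at a total of 80, 0.32 at 150, 0.59 at 300 and 0.80 at 500. For the same reason, adding a control arm to this 80-person study is not proposed.

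The cost is a few sentences and a more modest claim. Every planned analysis stays.
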